Immune responses to HIV-1 detected in acute infection are also thought to correlate with disease outcome. Loss of T cell function *in vitro* predicts progression to AIDS and a decrease in survival time (9). HIV-1-specific CD4⁺ helper responses are known to play a key role in maintaining effective immunity in a subset of individuals, termed long term non-progressors (LTNP), who successfully control viral replication, and fail to progress to AIDS despite ten or more years of infection (10). Furthermore, Rosenburg et al showed that HIV-1 specific proliferative responses to p24 are inversely correlated with viral load (11). CD4⁺ cells also most likely contribute to effective antiviral immunity by enhancing CD8⁺ CTL activity, increasing production of antiviral cytokines and potentiating humoral immune responses (reviewed in (12;13).

There is now abundant evidence to suggest that a vigorous CD8⁺ cytotoxic T lymphocyte (CTL) response, as well as a CD4⁺ response, is critical for controlling HIV-1 replication and preventing progression to AIDS. The importance of virus-specific CTL in HIV-1infection is illustrated by the observation that CD8⁺ CTL responses are readily detectable early after acute infection and coincide with the resolution of high levels of initial viremia (14-17). Furthermore, LTNPs have been shown to maintain a high level of CD8⁺ CTL activity to many epitopes of multiple antigens of HIV-1and decline in this antiviral response coincides with disease progression (18-22). A vigorous HIV-1 specific CD8⁺ CTL response following acute HIV-1 infection has been shown to be temporally associated with the control of viremia (23). Several investigators have shown that the detection of anti-gag CTL occurs early after seroconversion and that the level of anti-gag CTL response correlates with disease progression (24-26). Control of initial viremia is also crucial in the prevention of transmission of HIV-1 to sexual partners. Quinn and colleagues have recently shown that a strong correlation exists between viral load and the risk of transmission (27). A better understanding of the immunologic control of viral load will provide insights into modifying this important factor in HIV-1 transmission.

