We, the Principal Investigators, agree to conduct this study in full accordance with the provisions of this protocol. I agree to maintain all study documentation for a minimum of five years from the end of the study, unless directed otherwise by the HPTN Coordinating and Operations Center (CORE). Publication of the results of this study will be governed by HPTN and DAIDS policies. Any presentation, abstract, or manuscript will be made available by the investigators to the HPTN Manuscript Review Committee and DAIDS for review prior to submission.

We have read and understand the information in this protocol and will ensure that all associates, colleagues, and employees assisting in the conduct of the study are informed about the obligations incurred by their contribution to the study.

Name of Principal Investigator		
Signature of Principal Investigator	Date	
Name of Principal Investigator		-
Signature of Principal Investigator	Date	

HPTN 034 B HPTN EXPOSED-UNINFECTED LABORATORY SUB-STUDY **PROTOCOL SUMMARY**

Design:	Laboratory Sub-study for HPTN 034
Study Sites/Population:	Adult men and women who have been identified as HIV-1 uninfected sexual partners of recently HIV-1 infected participants in the HPTN 034A sub-study
Study Duration:	The sub-study is designed to run for the duration of the entire HPTN 034 funding period. Participants will be continuously enrolled and followed for up to two years, as funding allows.
Primary Objectives:	 (a) To determine if the detection of an HIV-1 -specific immune response in exposed uninfected individuals correlates with risk of subsequent HIV-1 infection. (b) To determine if immunologic genetic characteristics of exposed uninfected individuals correlates with risk of subsequent HIV-1 infection.
Primary Endpoints	 (a) HIV-1 antibody seroconversion (b) ELISPOT measurement of HIV-1 peptide-specific T lymphocytes (c) HLA-Class I MHC alleles
Secondary Objectives:	 (a)To determine if the detection of an HIV-1 -specific immune response in exposed-uninfected individuals correlates with the HIV-1 viral set point in individuals that subsequently become HIV-1 infected. (b) To compare the epitope specificity of the HIV-1-specific immune response of exposed-uninfected individuals with that of their recently infected partners. (c) To assess the feasibility of establishing a prospective cohort of recently infected individuals and their primary sexual partners for participation in HPTN HIV-1 prevention trials of discordant couples.

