2.0 STUDY OBJECTIVES AND DESIGN

2.1 Primary Objectives

- To determine if the detection of an HIV-1 -specific immune response in exposed uninfected individuals correlates with risk of subsequent HIV-1 infection.
- To determine if immunologic genetic characteristics of exposed uninfected individuals correlates with risk of subsequent HIV-1 infection.

2.2 Secondary Objectives:

- To determine if the detection of an HIV-1 -specific immune response in exposed uninfected individuals correlates with the HIV-1 viral set point in individuals that subsequently become HIV-1 infected.
- To compare the epitope specificity of the HIV-1 -specific immune response of exposed-uninfected individuals with that of their recently infected partners.
- To assess the feasibility of establishing a prospective cohort of recently infected individuals and their primary sexual partners for participation in HPTN HIV-1 prevention trials of discordant couples.

2.3 Study Design:

This is a prospective cohort study to be conducted at NARI. NARI will implement the study in accordance with this protocol, however additional studies and collaborations may be incorporated into this study with approval from the Executive Committee. NARI will document study data using standard data collection forms to be submitted to the HPTN Statistical and Data Management Center (SDMC).

An estimated 10-15 individuals/year who qualify as HIV-1 -exposed uninfected are expected to be enrolled in this study. To maximize efficiency and to utilize established systems for screening and follow-up, individuals who themselves are HIV-1 negative, but who have recently infected partners will be recruited from the ongoing 034 HPTN trial. Enrollment will be offered to all participants in HPTN protocols who fulfill the enrollment inclusion/exclusion criteria. Individuals will necessarily have had a previously documented negative HIV-1 test that will be confirmed by HIV-1 RNA PCR. Appendix A (Table 1) reflects the clinical and laboratory specimens that will be collected at each visit. In this protocol, only samples from exposed-uninfected individuals will be collected. Samples from seropositive and seronegative individuals enrolled in the 034AHPTN Early HIV-1 Infection Study Laboroatory Sub-study will serve as comparative controls for the assays performed in the exposed-uninfected study.

3.0 Study Population:

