3.1 Inclusion Criteria for HEPS Subjects

Eligible subjects would include individuals from the following population:

• HIV-1 uninfected partners of those enrolled in the 034A HPTN Early HIV-1 Infection Laboratory Sub-study.

All of the following must be fulfilled:

- Willing and able to provide informed consent
- \bullet > 18 years of age
- Willing to permit phlebotomy of four tubes of blood every three months for 24 months

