4.3 Laboratory Procedures

The laboratory procedures for this protocol are similar to what is proposed for the companion HPTN Early HIV-1 Infection Protocol. The training, technology transfer and quality control activities for these two protocols will be coordinated by the HCL.

4.3.1 Diagnosis of HIV-1 Infection:

NARI will utilize their own site-specific criteria for identifying individuals with HIV-1 infection. NARI will utilize commercially available HIV-1 antibody assay kits for HIV-1 screening. To be documented as HIV-1 antibody positive for the purposes of this protocol, eligible subjects must have a current positive HIV-1 antibody test and a negative HIV-1 antibody test result within the prior 6 months. A positive antibody test would be defined as either A) HIV-1 + by two different rapid tests B) HIV+ by two different serum ELISA tests C) HIV+ by one rapid AND one serum ELISA test or D) HIV+ by either a rapid test OR an ELISA AND by one HIV-1 western blot. As outlined above, individuals who are NOT HIV-1 antibody positive, based upon any of the above four criteria, will be eligible for enrollment in this protocol. In addition to identification of recent antibody seroconvertors, sites may utilize their own procedures for screening antibody negative specimens using either commercially available HIV-1 p24 Ag assays or HIV-1 PCR assays (see below) to determine eligibility for participation in this protocol.

4.3.2 HIV-1 PCR and Viral Load Testing:

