6.3 Statistical Considerations and Sample Size Calculations

Based upon assumptions outlined below for each of the two primary objectives, the target samples size for this study is a minimum of 20 subjects who are HIV-1 -exposed uninfected individuals with recently infected partners. For both primary objectives, frequency of HIV-1 infection will be an outcome measure. Patients will be divided into an infected and uninfected

cohort and compared with respect to the presence or absence of any prior detectable immune response as measured by Elispot.

6.3.1 Primary Objectives (a). Gag-specific ELISPOT Response vs. subsequent HIV-1 Infection.

For the purposes of comparing ELISPOT response to incidence of infections, gag-specific ELISPOT responses will be scored as positive or negative. As outlined in Appendix C, all experiments will be performed in duplicate wells. The IFN- γ -expressing spots will be calculated as the number of spots per 10⁵ stimulated PBMCs. Results will be expressed as net peptide-specific IFN- γ spots / 10⁵ PBMC. A positive peptide-specific response (responders) will be defined as a mean of greater than 5 spots above the mean spots of the mock-stimulated PBMC. Study participants will be expected to have multiple ELISPOT assays within the first 12 months of follow-up (See Appendix A). For the purpose of the sample size calculation, our initial analysis will compare HIV-infection with a positive response to any gag peptide, at any time point within 12 months since enrollment. Separate and similar analyses will be performed for recognition of HIV-1 subtype B gag and non-B gag peptides. Assuming a 20% seroconversion rate among the exposed uninfected cohort resulting in 20 acutely infected patients, we would have 80% power to detect at least a 25% difference in the proportion of individuals who elicit a gag immune response between the two groups (infected and uninfected).

Difference in proportion of patients with	Total sample size (unequal arms assuming
gag response	20% seroconversion rate)
20%	238
25%	138
30%	86

6.3.2 Correlation of HLA allelic expression with risk of subsequent infection.

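### 034B: with antibody-only testing during follow-up, an ELISPOT response caused by the infection itself can be scored as a prior response

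*Supplement*

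**What the plan says.** **Outcome.** The 034B Protocol Summary and section 5.1.3 list "a) HIV-1 antibody seroconversion (b) ELISPOT measurement of HIV-1 peptide-specific T lymphocytes" and HLA class I alleles as primary endpoints. Section 5.1.1 hypothesises that gag responders have a lower risk of later infection, over two years of follow-up.

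**Testing.** Participants must be "Willing to permit phlebotomy of four tubes of blood every three months for 24 months". Appendix A Table 1 schedules an antibody test at every visit (footnote 1), restricts RNA PCR to confirmed infection (footnote 2), and stores plasma at every visit for detuned-assay and viral-load work (footnote 3).

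**Entry.** Section 2.3 differs from footnote 2: "Individuals will necessarily have had a previously documented negative HIV-1 test that will be confirmed by HIV-1 RNA PCR". Section 4.3.1 adds that "sites may utilize their own procedures for screening antibody negative specimens using either commercially available HIV-1 p24 Ag assays or HIV-1 PCR assays", but only to determine eligibility.

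**Analysis.** Under 6.3 the infected and uninfected groups are "compared with respect to the presence or absence of any prior detectable immune response as measured by Elispot". Section 6.3.1 scores a response to any gag peptide, "at any time point within 12 months since enrollment". Neither section says what a response must precede.

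**Biology.** 034A section 1.1 describes CD8 responses in HIV-1 infection as "readily detectable early after acute infection and coincide with the resolution of high levels of initial viremia". 034A section 3.1 enrols people who are antibody negative or indeterminate but PCR or p24 positive.

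**The concern.** Someone infected a few weeks before a scheduled visit can still be antibody negative at that visit. By the documents' own account a CD8 response may already be present. That response results from the infection, yet the later positive antibody test makes it look like a response that came first. No rule removes it.

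Read literally, 6.3.1 goes further. Its 12-month clock runs from enrollment, so a response drawn after seroconversion in year 1 also qualifies unless the word *prior* in 6.3 is taken to govern. Section 4.3.5, in a sentence it shares with 034A, even calls for early and frequent ELISPOT once infection has been identified.

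Only people who become infected can be misclassified this way, and always from non-responder to responder. Primary objective (a) predicts fewer responders among the infected, so this error works against it. The same classification feeds secondary objective (a), prior response against viral set point. A larger or pooled sample would not remove it.

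**Working it through.** **1. The plan's own table.** Section 6.3.1 gives totals of 238, 138 and 86 for differences of 20, 25 and 30 points, at 80% power with 20% infected. It states no base rate or alpha. I took two-sided 0.05 (034A section 6.3.1 uses p=0.05) and two proportions with pooled variance at a 1:4 ratio. An infected rate of 60% against 80%, 85% and 90% gives 238.5, 138.4 and 84.7. The mirror set (40% v 20%, 15%, 10%) gives the same totals but contradicts the hypothesis. So 60% v 85% is inferred from the fit, not stated.

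Power at N=138 (27.6 infected, 110.4 uninfected):
- Pooled rate = 0.2 × 0.60 + 0.8 × 0.85 = 0.80.
- SE under the null = √(0.80 × 0.20 × (1/27.6 + 1/110.4)) = 0.0851.
- SE under the alternative = √(0.24/27.6 + 0.1275/110.4) = 0.0993.
- z = (0.25 − 1.96 × 0.0851)/0.0993 = 0.84, so power is 80%.

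**2. Share of infections with a window sample.** The documents give no window length *w* and no probability *q* that a window sample is ELISPOT positive. I assumed *w* = 21-42 days and *q* = 0.3-0.7.
- Visits are 91 days apart, so *w*/91 = 0.231-0.462 of people infected in year 1 give their last antibody-negative sample after infection.
- Only responses in the first 12 months count. At a constant hazard of −ln(0.8)/2 per year, year 1 holds (1 − √0.8)/0.2 = 0.528 of two-year infections.
- Affected share of all infections: 0.528 × (0.231 to 0.462) = 0.122-0.244.

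**3. Effect on the contrast.** Observed infected rate = 0.60 + 0.40 × share × *q*.

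| *w* (days) | *q* | infected rate | difference from 85% | power, N=138 |
|---|---|---|---|---|
| none | – | 60.0% | 25.0 | 0.80 |
| 21 | 0.3 | 61.5% | 23.5 | 0.759 |
| 21 | 0.7 | 63.4% | 21.6 | 0.700 |
| 42 | 0.3 | 62.9% | 22.1 | 0.715 |
| 42 | 0.7 | 66.8% | 18.2 | 0.580 |

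**4. Literal 6.3.1.** If every year-1 infection could add a post-infection response, the share is 0.528. Then 0.60 + 0.40 × 0.528 × (0.3 to 0.7) = 66.3-74.8%, a difference of 18.7-10.2 points.

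**5. The study as planned.** Section 6.3 sets a minimum of 20; section 2.3 expects 10-15 a year, so 20-30 over two years. At 20% that is 4-6 infections.
- Window samples: 4 × 0.122 to 6 × 0.244 = 0.5-1.5.
- Non-responders expected to be wrongly scored: 4 × 0.122 × 0.40 × 0.3 to 6 × 0.244 × 0.40 × 0.7 = 0.06-0.41.

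**6. An opposing bias.** An uninfected participant has five draws in months 0-12. Someone infected in quarter 1, 2, 3 or 4 has one, two, three or four draws before infection. Suppose there is no true effect, 45% are ever positive over five draws, and draws are independent.
- Per-draw rate = 1 − 0.55^(1/5) = 0.113.
- Ever-positive after 1-4 draws: 11%, 21%, 30%, 38%; year-2 infections: 45%.
- Weighted by 13.8%, 13.4%, 13.0%, 12.6% and 47.2% of infections, the infected group shows 34%.
- Adding the step 2 contamination to the year-1 quarters gives 37-47%, against 45%.

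With fully durable responses present from entry, the deficit disappears.

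**The case against.** The best defence is that 6.3 already says *prior* and 5.1.1 says *subsequent*, so a response caused by infection lies outside the intended comparison. Plasma is stored, RNA PCR follows confirmation, and a secondary endpoint refers to estimated time of infection, so back-testing is possible. Classification rules of this kind are often left to an analysis plan, and none is shown. Part of this stands: the intention is clear and the means exist. But 6.3.1 does state a counting rule, and following it misclassifies.

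Section 1.3.5 of the main protocol reports routine p24 screening of antibody-negative cohort members at this site. That could shorten the undetected window, but it is background and 034B does not adopt it for follow-up.

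A reader might infer several stronger things that the documents do not support:
- *034B formally dates infection by seroconversion.* It names seroconversion as an endpoint and gives no dating rule.
- *RNA is never tested before confirmation.* Section 2.3 calls for it at entry; if that applies, the gap is confined to follow-up.
- *Objective (a) is biased against protection overall, or will show harm under no effect.* Step 6 shows that the net sign depends on how durable responses are.
- *Power falls to 26-57%.* That needs 35% v 60%, which starts from 66% power at N=138 and does not reproduce the plan's table.
- *Secondary objective (b) is distorted too.* Section 5.2.2 compares infected participants with uninfected partners in discordant couples, which a seroconverter no longer fits.

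**Conclusion.** The gap is real. As written, 034B can score a response caused by infection as exposure preceding it, in the infected group only. Taken alone the error shrinks a protective contrast. At 60% v 85% and N=138 the loss is about 1 to 7 of 25 points. That rests on an assumed 3-6 week window, assumed 30-70% positivity, constant hazard and an inferred base rate. *q* could be lower early in the window, since the documents tie the response to resolving viraemia.

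In the 20-30 participants actually expected, the effect is about one sample and less than half a misclassified non-responder, in a sub-study that cannot reach its stated power anyway. The rule matters more if the data are later pooled. The net direction of bias is not determined, so the claim that protection is masked cannot be made. The correction is worth making because it is cheap.

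**What to change.** - **Back-test.** In 6.3.1 and Table 1 footnote 2, for each seroconverter run HIV-1 RNA on the stored plasma of the last antibody-negative visit, and of the visit before it if that is positive.
- **Define prior.** Count an ELISPOT result as prior only if it comes from an RNA-negative visit before seroconversion. This also closes the literal 12-month reading.
- **Missing plasma.** Do not drop the result automatically: on the assumed window, 54-77% of year-1 last-negative samples (1 − 0.462 to 1 − 0.231) were drawn before infection, and deletion would fall on the infected group alone. Report the analysis with and without that visit.
- **Equal opportunity to respond.** Compare the groups over the same visits at risk, for example by baseline response or response as a time-updated exposure.
- **Reconcile** footnote 2 with section 2.3 on RNA PCR at entry.

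Cost: one or two RNA tests per seroconverter on plasma already stored (4-12 tests for 4-6 seroconverters), short text changes, and a few reclassified ELISPOT results.

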1.0 INTRODUCTION

1.1 Background

AIDS, caused by infection with the human immunodeficiency virus 1 (HIV-1), is associated with enormous morbidity and mortality worldwide. Current estimates are that there are nearly 35 million people infected with HIV-1 globally, and that there are 15,000 new infections occurring daily (1). Developing countries shoulder nearly ninety five percent of all new HIV-1 infections. Although recent advances have been made in antiretroviral therapy for HIV-1 infection, there is no cure for AIDS, and the expense of drug therapy is prohibitive for most of the population. For this reason, clinical HIV-1 prevention trials sponsored by NIAID and the HPTN and HVTN are ongoing and in development. These trials include prevention through antiretroviral drugs, microbicides, behavioral approaches, barrier and other contraceptive/STD prevention methods, vaccines (in perinatal settings), chemoprophylaxis, treatment of sexually transmitted diseases, and combined approaches (2).

Despite important advances in understanding and identifying critical host and viral factors that can influence acquisition of HIV-1 infection, viral load and disease progression, the goal of translating this information into effective prophylactic treatments and vaccines has not been achieved. Toward this end, many immunologic studies have been done on cohorts of individuals that exhibit relative resistance to infection with HIV-1 despite multiple high-risk exposures. Standard HIV-1 IgG ELISA assays and Western blots are negative in these subjects, as are sensitive HIV-1 RNA PCR assays in the peripheral blood. Because there remains the possibility that persistent infection has been established in these cases, but viremia has been controlled to levels below the limits of detection these individuals are often referred to as Highly Exposed, Persistently Seronegative (HEPS). Resistance to HIV-1 infection has been observed in sex partners of HIV-1 infected persons (3-7), infants born to HIV-1 infected mothers (8-11), health care workers occupationally exposure to HIV-1 -contaminated body fluids (7:12) and commercial sex-workers (CSWs) (3;4). It has been hypothesized that protection against human immunodeficiency virus HIV-1 infection may result from either acquired host immunity, inheritance of a dysfunctional HIV-1 co-receptor (such as CCR5), a low or attenuated virus inoculum, or host genetic factors such as HLA genotype (13;14). Thus far, no evidence exists for a significant role for CCR5 $\Delta 32/\Delta 32$ mutation in non-Caucasian North American populations (6;7;15). Because more than 80% of HIV-1 infections world-wide occur through heterosexual transmission, it has been hypothesized that the mechanism of protection in these individuals is mediated, in part, by cellular immune mechanisms present at mucosal sites of exposure (16).

The association of HIV-1 -specific CTL with non-progressive disease in HIV-1 infected persons, as well as the increased frequency of certain HLA class I alleles in HEPS populations, has led several groups to look for HLA class I restricted, HIV-1 -specific CTL in these groups(17-24). HIV-1 -specific CTL have now been described in the peripheral blood of HEPS (16). Studies by several investigators have shown that HIV-1 -specific CD8⁺ T cells can be detected in the peripheral blood of 30-60% of HEPS tested. These CD8⁺ responses have been measured both in conventional CTL lysis assays (20) as well as IFN- γ ELISPOT assays (21). Responses to multiple HIV-1 antigens were detected including env, gag, pol and nef. Interestingly, HIV-1 -specific CTL have recently been demonstrated in the genital tract, the

likely site of viral exposure, in a subset of a HEPS cohort in Nairobi (21). It has been hypothesized that a primed CTL response at the site of exposure would be more relevant in protection against incident HIV-1 infection than in blood, where HEPS CTL responses have been previously described (21). These CD8⁺ cells were most likely intraepithelial memory T lymphocytes generated in secondary lymphoid organs that localize to epithelial sites upon reexposure to antigen (25). Overall, these responses (both mucosal and peripheral) tended to be lower and not as durable as those seen in seropositive individuals. Nonetheless, the detection of HIV-1 -specific CTL in the genital tract of these HEPS suggests that these responses may be important in mediating protective immunity against heterosexual HIV-1 acquisition.

Resistance to infection with HIV-1 based on a noncytolytic CD8⁺ T cell-mediated mechanism has also been reported. Stranford et al described a CD8⁺-mediated, noncytolytic anti-HIV-1 activity that was seen in the vast majority of individuals most recently exposed to the virus (within 1 year), and was potent enough to inhibit *in vitro* infection of subject's PBMC (26). Paxton et al, showed that resistance to infection of CD4⁺ lymphocytes from HEPS was associated with the activity of C-C chemokines such as RANTES, MIP1 α , and MIP-1 β (27-29). Other HIV-1 -specific immune responses have also been observed in HEPS cohorts such as IgA in mucosa (30) (31;32)and serum (33), and serum antibodies to HLA molecules (34;35) and CD4 (36). The contribution of these mechanisms to resistance to HIV-1 infection remains unclear.

As discussed above, published studies thus far have detected CTL in the blood of approximately 30-60% of HEPS individuals examined. The fact that HIV-1-specific CD8⁺ immune responses are not detected in all HEPS tested suggests that other mechanisms could be involved in this protection, that the current assays used to detect the CD8⁺ immune response lack the sensitivity to detect these responses, or that only 30-60% of HEPS are actually exposed to HIV-1. One of the problems that exists in current assays systems is that there is a significant lack of defined CTL epitopes in individuals exposed to non-clade B strains of HIV-1 (37). Furthermore, it is likely that epitopes previously characterized in seropositive individuals are not necessarily going to be the same as those recognized by HEPS. For this reason, an important goal of the HPTN immunology core group is to enroll potential subjects identified as HEPS and ultimately test specimens for HIV-1 -specific CD8⁺ mediated immune responses using clade-specific antigens and the most current and sensitive technologies available.

